10.3 Safety and efficacy evaluations

The primary endpoint, average glucose, will be assessed by examining blood glucose (mg/dL) area under curve as measured by CGM. Glucose data on days without canagliflozin treatment will serve as a control.

The secondary endpoints of safety and tolerability and urinary glucose excretion will also be assessed. Safety and tolerability will be measured by adverse event reporting, blood pressure monitoring, and by comparing treatment tolerability survey results with control tolerability results through subjective surveys. Urinary glucose excretion will be measured by at-home glucose testing strips.

11 Investigational Product

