IRCM-2024-384

Jan. 24, 2024

Title: The Efficacy and Tolerability of Canagliflozin in Healthy Individuals

Comparing Dosing Protocols of Canagliflozin for use as a Gerotherapeutic

Protocol Number:

ALRx008

Test Drug: Canagliflozin, also known as Invokana.**Indication:** For use in healthy, non-diabetic individuals (ages 18-85).**Study Design:** Prospective, non-randomized trial to evaluate tolerability and efficacy in reducing baseline glucose and glucose spikes in non-diabetic individuals.**Site:** This is a decentralized trial. Participants can be located in any of the 50 states of the USA. All participation will be via telemedicine using the AgelessRx website (agelessrx.com).**Sponsor Name, Address, and Telephone Number:**

AgelessRx

Address: [name]

[contact]

[contact]

Email: [contact]**Research Coordinator**

[name]

Address: [name]

[contact]

Email: [contact]**Principal Investigator**

[name]

Address: [name]

[contact]

[contact]

Email: [contact]**Institutional Review Board of the Institute of Regenerative and Cellular Medicine**

[name]

[contact]

Email: [contact]**Compliance:**

The study will be conducted in accordance with standards of Good Clinical Practice, as defined by the International Conference on Harmonisation and all applicable federal and local regulations.

Date of Protocol: January 16th, 2023**Confidential Information**

The information contained within this protocol is confidential and may not be used, divulged, published, or otherwise disclosed without the prior written consent of AgelessRx.

1. Signature Page

I have read this clinical protocol and confirm that to the best of my knowledge it accurately describes the design and conduct of the study titled "The Efficacy and Tolerability of Canagliflozin in Healthy Individuals: Comparing Dosing Protocols of Canagliflozin for use as a Gerotherapeutic".

[name]

Date 01/17/2024

2. Synopsis

Name of Sponsor/Company: AgelessRx
Name of product: Canagliflozin (trade names: Invokana)
Title of study: The Efficacy and Tolerability of Canagliflozin in Healthy Individuals Comparing Dosing Protocols of Canagliflozin for use as a Gerotherapeutic

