Objectives: Primary: To measure the effects that canagliflozin intervention has on reducing average glucose in healthy individuals. Secondary: To assess the tolerability and side effects and urinary glucose excretion following the pulsatile dosing protocol.
Methodology: 
1. Candidates will be offered participation through word of mouth and AgelessRx platform.2. Once screened and enrolled, participants will be randomized into one of two arms (A and B) and provided with all items included in the materials list below.3. Arms A & B:
a Day 0: Participants will attach a continuous glucose monitor (CGM) and follow instructions for calibration period.b Day 1 – 14: Participants will take morning blood pressure readings, and keep dietary intake journal via Lifesum.c Day 7: Participant completes Urine Collection Kit #14. Arm A:
a Day 8 - 14: Participants take 100mg Invokana (canagliflozin) with first meal daily.b Day 15: 24h after final dose, Participant completes Urine Collection Kit #2c Day 16: 48h after final dose, Participant completes Urine Collection Kit #3d Day 17: 72h after final dose, Participant completes Urine Collection Kit #45. Arm B:
a Day 8 - 14: Participants take 150mg Invokana (canagliflozin) with first meal daily, every other day for a total of 4 doses.b Day 15: 24h after final dose, Participant completes Urine Collection Kit #2c Day 16: 48h after final dose, Participant completes Urine Collection Kit #3d Day 17: 72h after final dose, Participant completes Urine Collection Kit #4
Number of subjects planned: Up to 20 healthy individuals via telehealth administration, 10 individuals in each Arm.

Diagnosis and main criteria for inclusion: Subjects will be healthy and of any sex, any ethnicity, and any age from 18-85. Participants must be approved by AgelessRx Medical Team for use of canagliflozin. They also require a CGM-compatible mobile device ([defined here](#))

Test product, dose, and mode of administration (proposed): The tablets will be from the brand Invokana and have a dosage of 100 mg or 300 mg per tablet. Investigational drugs are to be administered orally. Investigational drugs will be provided by Curexa Pharmacy, [name]

Duration of treatment: 7 days

Criteria for evaluation:

Efficacy:

- CGM data
- Urinary glucose

Safety:

- Tolerability

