6.4 Rationale and Hypothesis

Canagliflozin is a prime candidate to reduce glucose spikes and blood sugar. It has consistently acted to treat type 2 diabetes and has been shown to improve biomarkers such as fasted glucose and glucose spikes.

The current FDA-approved use of the drug is for use together with diet and exercise to treat type 2 diabetes. Canagliflozin is sometimes used in combination with insulin or other diabetes medications taken orally. It is routinely prescribed at equal or higher doses than the ones proposed in this trial.

AgelessRx Trial doses: 100 mg and 150 mg doses, taken every day and every-other day, respectively.

FDA-approved dose: Maximum recommended dose: 300 mg once daily.

Some possible side effects at the FDA-approved doses include hypoglycemia, indigestion, nausea, UTI, increased urination or thirst, hypotension, ketoacidosis, dehydration, and headache. The doses we propose have potential for some side effects, though the drug is generally well tolerated.

This trial will use a lower dose than the maximum one recommended by the FDA. We are using a maximum of 150 mg in one day vs the maximum of 300 mg each day recommended by the FDA. At this smaller dose, side effects are less common⁸. This dose has been shown to be generally safe.

Our hypothesis is three-fold:

1. Canagliflozin can be used safely and is well tolerated at doses of 100 mg per day or 150 mg every two days in healthy, non-diabetic individuals.
2. Usage of canagliflozin at these doses can effectively reduce glucose spikes (and their detrimental effects) and blood sugar levels measured by CGM in a healthy population.
3. Usage on alternate days will be effective as measured by our endpoints.

7. Objectives

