8.1 Study Design

This study is designed to mitigate the effects of glucose with intermittent oral Canagliflozin for healthy, non-diabetic volunteers of any sex who enroll in the study. The volunteers can be within 18-85 years of age at the time of enrollment. Participants will provide informed consent via AgelessRx EMR. If eligible, prescriptions will be provided online through the AgelessRx website (www.agelessrx.com). Participants will be randomized into two arms: Arm A will take 100 mg of canagliflozin each day for a total of 7 doses, while Arm B will take 150 mg of canagliflozin every other day for a total of 4 doses. Participants in Arm B will also be provided a pill cutter to use throughout the trial on the 300mg tablet.

All participants will begin the trial on the day that they apply a continuous glucose monitor (considered Day 0) and will be asked to take daily blood pressure reading. After one week of baseline readings, both arms will start their canagliflozin dosing protocols.

Participants will be asked to complete 7 total surveys to outline side effects and tolerability, one each day starting after their canagliflozin consumption.

Participants will be asked to complete a dietary intake journal through Day 0 – Day 14. Lifesum (<https://lifesum.com/>) should be used to track Carbohydrate/Protein/Fat consumption. Participants will share their dietary intake journal twice over their participation (Day 7 & Day 14).

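### The title promises a comparison of dosing protocols, but no objective, hypothesis or analysis sentence states an Arm A versus Arm B contrast

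*Combined protocol and SAP*

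**What the plan says.** The title of the combined protocol and SAP carries the words "Comparing Dosing Protocols of Canagliflozin for use as a Gerotherapeutic". Section 8.1 states "Participants will be randomized into two arms", and the Synopsis says the same. The planned size is "Up to 20 healthy individuals via telehealth administration, 10 individuals in each Arm". The cover page, however, describes the study as a "Prospective, non-randomized trial to evaluate tolerability and efficacy in reducing baseline glucose".

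The efficacy contrast is set out in Section 10.3: "Glucose data on days without canagliflozin treatment will serve as a control". Section 7.1 likewise frames the primary objective as glucose on drug against glucose off drug. The third hypothesis in Section 6.4 reads "Usage on alternate days will be effective as measured by our endpoints"; it does not say how alternate-day use should compare with daily use.

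The Synopsis assigns CGM readings to an analysis of variance, and Section 13 assigns blood tests to one. Neither names a factor.

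**The concern.** A trial that announces a comparison of two regimens and allocates people between them needs an estimate of the difference between them. This plan states none. If only on-drug versus off-drug contrasts are produced, the material for comparing regimens is one result per arm. Two inferences then become tempting: that one regimen worked and the other did not, or that both worked and so are alike. Neither follows from separate within-arm tests. The week of baseline glucose that could sharpen a direct comparison is collected but given no role in one.

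The wording of Section 10.3 adds a second problem. Arm B has undosed days inside the treatment week and Arm A has none. Read literally, those days could count as control in Arm B only, so the two within-arm effects need not measure the same thing.

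**Working it through.** **Inputs from the documents.** 10 per arm (Synopsis). Untreated week on Days 1-7 and treatment on Days 8-14 in both arms (Synopsis; Section 8.1). Arm A: 7 doses in 7 days, so 0 undosed days. Arm B: 4 doses in 7 days, so 7 − 4 = 3 undosed days.

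**Not in the documents.** Significance level, power, effect size, SD and margin. There is therefore no sample-size calculation to reproduce. Assumed below: two-sided 5%, normally distributed within-person changes, independent arms, and a standardised effect *d* = mean change / SD of change, shown over a range.

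**Step 1: does any sentence compare the arms?**

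| Place | Contrast stated |
|---|---|
| Title | Dosing protocols compared |
| Synopsis and Section 7 objectives | Effect of the drug; tolerability; urinary glucose |
| Section 6.4 hypotheses | Safe; effective; alternate-day use effective |
| Section 10.3 | Off-drug days as control |
| Synopsis statistics, Section 13 | Analysis of variance, no factors |

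Only the title is comparative.

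**Step 2: separate verdicts when the regimens are equally effective.** The power *p* of a paired t-test with n = 10 comes from the noncentral t distribution (9 df, noncentrality *d*√10). The chance that exactly one arm is significant is 2*p*(1 − *p*), computed from unrounded powers.

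| *d* | *p* | Exactly one arm significant |
|---|---|---|
| 0.3 | 0.136 | 24% |
| 0.5 | 0.293 | 41% |
| 0.7 | 0.506 | 50% |
| 1.0 | 0.803 | 32% |
| 1.2 | 0.920 | 15% |
| 1.5 | 0.987 | 2.5% |

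A simulation of 100,000 runs gave 49.6% at 0.7 and 31.7% at 1.0. A direct between-arm t-test rejected in 4.9% and 5.0% of the same runs, as it should.

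**Step 3: the opposite error.** With both true effects at 1.5 SD, both arms are significant with probability 0.975. With effects of 1.5 and 2.0 SD, the probability is 0.987. The double verdict barely distinguishes equal from unequal regimens.

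**Step 4: precision of a direct contrast.** The 95% half-width for the difference in change is t(0.975, 18) × √(2/10) = 2.101 × 0.447 = 0.94 SD. If the SD of change is 4 to 8 mg/dL (assumed), that is 3.8 to 7.5 mg/dL. Power for a 0.5 SD difference is 19%; 80% power needs a difference of 1.32 SD.

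**Step 5: gain from baseline adjustment.** With equal variances in the two weeks, the variance of ANCOVA relative to a change score is (1 + ρ)/2 × (1 + 1/16). The second factor is the cost of estimating the slope with 20 people (20 − 4 = 16).

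- ρ = 0.5: 0.75 × 1.0625 = 0.80
- ρ = 0.7: 0.85 × 1.0625 = 0.90
- ρ = 0.9: 0.95 × 1.0625 = 1.01

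The gain is thus about 20%, 10% and nil for these assumed correlations.

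**The case against.** The strongest reply is that the stated aims are not comparative. Every objective and hypothesis asks whether the drug works or is tolerated, and off-drug days are the matching control for that. This stands, and it is why rewording the title is an acceptable repair. It does not rescue a plan that keeps the title.

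A second reply is that the analysis of variance may be meant to include an arm or arm-by-period term. It may; writing the term down would then be the fix. A third is that 20 people are too few to compare regimens. That argues for reporting an interval and saying it is wide.

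Four stronger readings are tempting but unsupported:

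- A reader might infer that the plan prescribes two within-arm tests and a comparison of their p-values. It states no such tests, no significance level and no success rule, and the arms could equally be pooled. Even the within-person nature of the control is inferred, from the shared baseline week and the absence of a placebo group (Section 11.2).
- A reader might infer that Section 8.1 randomises for the sake of comparison. It gives no such reason.
- A reader might infer that only the between-arm contrast removes changes common to both arms from week 1 to week 2. Arm B's dosed versus undosed days within Days 8-14 would also remove them, subject to carry-over.
- A reader might infer that a false difference is likely. That depends on an effect size the documents do not give; at 1.5 SD the chance is 2.5%.

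**Conclusion.** The concern holds as an omission: as written, the plan does not specify an answer to the question in its title. If within-arm results were used instead, equally effective regimens would give split verdicts 24% to 50% of the time for effects of 0.3 to 1.0 SD, falling to 15% at 1.2 and 2.5% at 1.5. At large effects two significant results say almost nothing about similarity. These figures rest on the assumed two-sided 5% level, normality and the effect range shown; the absence of a stated contrast rests on the text alone. A direct contrast can be estimated from data already planned, though only imprecisely. Its standing as a randomised comparison depends on resolving the cover page's conflict with the Synopsis and Section 8.1. The plan should be changed on this point.

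**What to change.** First reconcile the cover page with the Synopsis and Section 8.1 on whether allocation is randomised. If it is not, the arm contrast loses its protection against confounding.

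Then add to Sections 10.3 and 13:

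*The regimens will be compared by the between-arm difference in each participant's mean CGM glucose over the whole of Days 8-14, using the same window in both arms. Arm B's undosed days in that window belong to the treatment period and are not control days. The analysis will be ANCOVA adjusting for the participant's Days 1-7 mean, with one value per participant per period. The result will be reported as an estimate with a 95% confidence interval. Separate within-arm tests will not be used to call one regimen better or the two similar.*

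Conclusions should be worded as regimen against regimen, since the arms differ in both dose and frequency. If no comparison is intended, remove it from the title instead.

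The cost is a few sentences and no new data. The downside is a wide interval, with a half-width of about 0.94 SD of the change before any gain from adjustment; the plan should say so in advance.

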7.1 Primary Objective

To measure the effects that Canagliflozin intervention has on blood glucose at the tested doses. This will be measured by observing glucose spikes following a high-carbohydrate meal at the tested doses, as well as by studying baseline glucose levels with and without canagliflozin.

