11.3 Dosing and Administration

11.3.1 Dose Escalation, Dose Adjustments, Stopping Rules

Participants will receive 100 mg tablets or 300 mg tablets, broken in half. There will be no dose escalation in this study. Dose adjustments or discontinuation of the drug can be made based on adverse events in a participant, which will be discussed in a phone call between the participant and Research Coordinator.

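### Section 10.3 defines control days by whether drug was taken, so dosing-week days lost to side effects become control days and the primary contrast no longer reflects the assigned regimens

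*Combined protocol and SAP*

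**What the plan says.** Section 10.3 names the outcome: "The primary endpoint, average glucose, will be assessed by examining blood glucose (mg/dL) area under curve as measured by CGM". The sentence after it is the only definition of the comparator in the document: "Glucose data on days without canagliflozin treatment will serve as a control". Section 7.1 frames the objective in similar terms, in part as "studying baseline glucose levels with and without canagliflozin".

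On timing, Section 8.1 says: "After one week of baseline readings, both arms will start their canagliflozin dosing protocols". The Synopsis places dosing on Days 8-14. Section 8.1 also gives the schedules: "Arm A will take 100 mg of canagliflozin each day for a total of 7 doses" and "Arm B will take 150 mg of canagliflozin every other day for a total of 4 doses". Arm B therefore has 3 scheduled off days inside its dosing week.

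Section 11.3.1 adds: "Dose adjustments or discontinuation of the drug can be made based on adverse events in a participant". No section says how glucose readings are classed after a missed dose or a stop. The Synopsis plans an analysis of variance of CGM readings, and Section 13 plans one of blood tests. Neither names the treated days, an analysis set or a rule for missed doses.

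The hypotheses in Section 6.4 are about using the two regimens. The second reads in part: "Usage of canagliflozin at these doses can effectively reduce glucose spikes". The third concerns alternate-day use.

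**The concern.** A day on which a scheduled dose was skipped, or that follows a stop, is literally a day without drug. Under 10.3 it moves into the control, although it belongs to the week in which the participant was assigned to treatment. Where an adverse event caused the stop, the sorting depends on how that participant tolerated the drug. Randomization does not protect a comparison between arms that is built on such sorting.

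Two things follow. Readings that still carry some drug effect can enter the control. And if the missed days also leave the treated mean, the result describes only the days on which people managed to take the drug. Someone who stopped after one dose could then show the same effect as someone who finished the week. The hypotheses ask about the regimens as assigned, and with 10 people per arm a few early stops can move an arm mean.

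**Working it through.** The plan gives no effect size, variability, power or stopping rate, so there is no figure to reproduce. The check is arithmetic on days.

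**From the documents:** 7 baseline days and 7 assigned days (8.1, Synopsis); 7 doses in Arm A and 4 in Arm B (8.1); 10 participants per arm (Synopsis).

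**Assumed:** the effect is d on every dosed day and 0 on baseline days; a fraction of d may persist on days after a dose; the example participant in Arm A stops after k = 3 doses; 2 or 4 of 10 do so. None of these values is in the documents.

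**Formulas.** Let u be the number of undosed days in Days 8-14, and C the sum of the carryover fractions on those days.

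- As-taken contrast (dosed days against all undosed days): d × [1 − C/(7 + u)]
- Assigned-week contrast (Days 8-14 against Days 1-7): d × (k + C)/7

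For k = 3, u = 4 and the control holds 7 + 4 = 11 days.

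| Carryover after the last dose | C | As-taken | Assigned week |
|---|---|---|---|
| None | 0 | 1 − 0/11 = 1.00d | 3/7 = 0.43d |
| 50% on the first off day | 0.5 | 1 − 0.5/11 = 0.95d | 3.5/7 = 0.50d |
| 50%, 25%, 12.5% over three days | 0.875 | 1 − 0.875/11 = 0.92d | 3.875/7 = 0.55d |
| 100% for three days | 3 | 1 − 3/11 = 0.73d | 6/7 = 0.86d |

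**Arm mean.** If m of 10 stop after 3 doses and the rest complete, each contrast averages to [(10 − m) × 1 + m × (individual value)]/10.

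- No carryover, m = 2: 1.00d against (8 + 2 × 3/7)/10 = 0.886d, overstated by 13%.
- No carryover, m = 4: 1.00d against (6 + 4 × 3/7)/10 = 0.771d, overstated by 30%.
- 50% on the first off day, m = 2: (8 + 2 × 0.955)/10 = 0.991d against (8 + 2 × 0.50)/10 = 0.900d, overstated by 10%.
- 100% for three days, m = 2: (8 + 2 × 0.727)/10 = 0.945d against (8 + 2 × 0.857)/10 = 0.971d, understated by 3%.

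**How much rests on the unstated half.** Suppose missed days joined the control but also stayed in the treated mean. The contrast would be (3 + C)/7 − C/11. With no carryover this is 0.43d, the assigned-week value, so there is no distortion. With full three-day carryover it is 0.857 − 0.273 = 0.58d against 0.86d, a dilution. The 13% and 30% figures therefore need missed days to leave the treated mean.

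**Arm B with every dose taken.** The same sentence puts its 3 scheduled off days in the control. With no carryover that gives 1.00d as taken, against 4/7 = 0.57d over the assigned week. A repair must therefore say where these days belong.

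**The case against.** **The sentence defines only the control.** Section 8.1 describes a baseline week followed by a dosing week, and a reader could take the contrast to be simply one against the other. It is true that the plan never states that the treated mean contains dosed days only; that is an inference. But nothing limits the control to the baseline week, and the one sentence that defines it covers stopped and skipped days as it stands.

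**An on-drug contrast is a fair question** for a seven-day study of up to 20 people, and it matches the with-and-without framing of 7.1. This stands as a reason to keep it as a supportive analysis.

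**A reader might infer that poor tolerability would be hidden.** The documents do not support that. Tolerability is a secondary objective, with daily surveys and adverse event reporting of its own. What is affected is the meaning of the glucose result.

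**A reader might also infer that the rule always inflates the effect, or that the worse-tolerated arm always gains.** The documents do not establish this either. Urine glucose is collected 24, 48 and 72 hours after the last dose, so persistence is an open question in this trial, and with full three-day carryover the direction reverses.

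**The stopping rates have no source.** That is correct. Section 6.4 calls the drug generally well tolerated, and 2 or 4 of 10 are illustrations only.

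**An illness example might seem to strengthen the case, but it does not.** Assume no drug effect and two skipped days at +10 mg/dL. The as-taken rule shows a false fall of 20/9 = 2.2 mg/dL, and the assigned week shows a rise of 20/7 = 2.9 mg/dL. The assigned-week analysis is no closer to zero, so the case for it rests on matching the hypotheses.

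**Conclusion.** The point holds as a defect in how 10.3 defines the control. Read literally with 11.3.1, the rule turns dosing-week days into control days for reasons tied to tolerability, and it can place drug-affected days in the control. The contrast then does not answer the regimen questions in 6.4.

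The size is conditional. For an early stopper in Arm A, the gap between the as-taken and assigned-week contrasts runs from 0.57d too high (no carryover) to 0.13d too low (full three-day carryover). These figures assume a constant daily effect and that missed days leave the treated mean. If nobody misses or stops a dose, Arm A is unaffected. The wording should be corrected, because the repair costs little and uses days already in the schedule.

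**What to change.** In 10.3, name the pre-dose baseline days (Days 1-7) as the only control, and the assigned dosing week (Days 8-14) as the treated period in both arms, whether or not each dose was taken, changed or stopped. No day from Day 8 on then becomes control, and Arm B's scheduled off days count as part of its regimen. State that CGM wear continues to its planned end after a stop. Report the on-drug-days contrast as supportive, with the number of participants and days affected. None of this alters who stops or when.

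The cost is protocol and SAP wording. The primary estimate may be somewhat smaller if doses are missed. For Arm B it becomes a whole-week average even with full adherence (0.57d rather than 1.00d with no carryover). The supportive contrast needs a daily record of intake. The contents list an Accountability section (11.3.4), but the body moves from 11.3.3 to 11.4 and describes no dosing log, so a dose-taken item could be added to the daily survey.

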11.2 Control Drug

No placebo will be used in this trial.

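### The tolerability surveys are to be compared with a control, but every scheduled survey follows the first canagliflozin dose and no control is defined for them

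*Combined protocol and SAP*

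**What the plan says.** Section 10.3 names three sources for safety and tolerability: adverse event reporting, blood pressure, and "comparing treatment tolerability survey results with control tolerability results through subjective surveys".

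The survey schedule is in Section 8.1: "Participants will be asked to complete 7 total surveys to outline side effects and tolerability, one each day starting after their canagliflozin consumption". The same section places dosing after the baseline week: "After one week of baseline readings, both arms will start their canagliflozin dosing protocols".

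The Synopsis (Methodology) lists what participants do on Days 1–14: "Participants will take morning blood pressure readings, and keep dietary intake journal via Lifesum". It adds a CGM from Day 0 and a urine kit on Day 7, and mentions no survey. Arm A doses daily on Days 8–14. For Arm B over the same days the Synopsis says "Participants take 150mg Invokana (canagliflozin) with first meal daily, every other day for a total of 4 doses".

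On controls, Section 11.2 states "No placebo will be used in this trial". The only control defined anywhere is in Section 10.3, and it is for glucose: "Glucose data on days without canagliflozin treatment will serve as a control". Section 13 gives no analysis for the surveys.

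**The concern.** Section 10.3 needs two sets of survey results, one on treatment and one under control. Section 8.1 supplies only surveys completed after drug intake. There is no untreated arm to provide the other set, and the control rule in Section 10.3 is worded for glucose data only.

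Tolerability is part of the secondary objective (Section 7.2) and of the first hypothesis (Section 6.4). The side effects listed in Section 6.4 include headache, indigestion, nausea and increased urination or thirst, all of which people may have without the drug. Section 9.2 admits people aged 18–85 with well-managed chronic disease, and Section 11.4 has participants continue their other medications, so some existing complaints are to be expected. With no survey before the first dose, the survey results have no reference level against which to judge complaints that begin on canagliflozin. The missing data cannot be collected once a participant has started dosing.

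**Working it through.** This is a count of survey days against dosing days. No error rate or sample-size formula is involved.

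**Inputs**
- Participants: up to 20, 10 per arm (Synopsis).
- Surveys: 7 per participant, one a day, starting after canagliflozin is taken (Section 8.1).
- Arm A dosing days: 8, 9, 10, 11, 12, 13, 14, which is 7 doses (Synopsis, Section 8.1).
- Arm B dosing days: 8, 10, 12, 14, which is 4 doses (Synopsis, Section 8.1).
- Section 8.1 gives no day numbers for the surveys.

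**Reproducing the plan's figure.** One survey a day over Days 8–14 gives 14 − 8 + 1 = 7, the stated number. This is the likelier reading. A start on the day after the first dose, Days 9–15, also gives 7 and is possible.

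**Pre-treatment surveys.** These would have to fall before Day 8. Both readings give 0 per participant, hence 0 of 7 × 20 = 140.

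**Surveys on undosed days**, in case the glucose rule was meant to cover surveys too:

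| Survey days | Arm A, undosed days | Arm A total | Arm B, undosed days | Arm B total | Both arms |
|---|---|---|---|---|---|
| 8–14 | none | 0 × 10 = 0 of 70 | 9, 11, 13 | 3 × 10 = 30 of 70 | 30 of 140 |
| 9–15 | 15 | 1 × 10 = 10 of 70 | 9, 11, 13, 15 | 4 × 10 = 40 of 70 | 50 of 140 |

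**Time since the last dose.** In Arm B, Days 9, 11, 13 and 15 follow doses on Days 8, 10, 12 and 14. In Arm A, Day 15 follows the dose on Day 14. Every undosed survey day is therefore exactly one day after a dose. The trial itself collects urine for glucose at 24 and 48 hours after the final dose and again later: "72h after final dose, Participant completes Urine Collection Kit #4". The plan thus treats the duration of effect after a dose as something to be measured, so the day after a dose has not been shown to be drug-free.

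**The case against.** The strongest counter-argument is that Section 10.3 already has a control rule, days without canagliflozin, and that a reader would naturally carry it over to the surveys. Arm B would then have three control surveys per participant on the Days 8–14 reading, so some comparison could be made. That is arithmetically right, but the text limits the rule to glucose. On that reading Arm A has no such survey, and Arm B's all fall the day after a dose. At best the result is a partial, post-dose contrast in one arm. It is also true that sampling urine at 24–72 hours does not show that symptoms persist. It shows only that the question is open, which is enough to make those days unsafe as an untreated reference.

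Other points limit the consequence without removing the gap:
- The survey questions are not in the documents. If they ask about new or changed symptoms, they would separate old complaints from new ones in part.
- Candidates complete a medical intake before treatment (Section 10.1), and monitoring forms collect adverse events (Section 12.3.1). Neither is called a control survey, and neither has a stated baseline symptom schedule.
- The design figure and the consent text are not available to us, so a baseline survey mentioned only there cannot be excluded. It would, however, conflict with the total of seven in Section 8.1.
- The Days 9–15 reading is the weaker one, since Day 15 lies beyond the two weeks of enrollment in Section 10.2, although urine kits also run past that point. The main result, no pre-treatment surveys, is the same on either reading.

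**Conclusion.** The concern holds. Sections 8.1 and 10.3 conflict: following the written schedule exactly produces no pre-treatment survey in either arm, and the control for the survey comparison is undefined. The 140 planned surveys are a maximum, because enrollment is up to 20. The finding of zero depends neither on the number enrolled nor on which survey days were intended. It rests on the readable text being complete as to survey timing.

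The scope is limited. One of three components of a secondary endpoint is affected, and with it part of the evidence for the first hypothesis. Blood pressure is recorded from Day 1 and has a true baseline week, and adverse event reporting stands. The change should be made before any participant is dosed. It does not call the whole safety assessment into question.

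**What to change.** In Section 8.1, give the survey days by number and send the same survey during the existing baseline week, Days 1–7, as well as during treatment. In Section 10.3, define control tolerability as the Days 1–7 surveys in both arms, compared within participant with the treatment surveys, and state that between-dose and post-dose days do not serve as control.

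The cost is up to seven more short surveys per participant, up to 7 × 20 = 140 in all, in a week when participants already record blood pressure and diet daily. Fewer baseline surveys would also supply a pre-treatment value. Seven against seven has the advantage of giving each period the same number of chances to report a complaint. The comparison would remain open-label and before–after, exposed to expectation and time effects, so it would improve attribution to the drug without settling it.

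If baseline surveys are not added, delete the control comparison from Section 10.3 and report the seven surveys descriptively by arm and day. That needs only a text change, but gives up the comparison.
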